7.2.5 Baseline Descriptive Statistics

The demographic measurements and general characteristics (age, gender, height, BMI, EDSS scores) of the participants in the two groups will be compared at baseline using two-sample t-tests for continuous variables and the chi-square test for categorical variables. In the inferential tests statistical significance will be set at 5% and all p-values is two-sided.

7.2.6 Analysis of the Exploratory Endpoint (s)

The relationship between MRI measures previously collected at Standard of Care visits (total brain volume, white and gray matter volume, and degree of brain atrophy) and the participant's level of improvement (e.g. % change in gait and balance parameters such as walking speed and sway area) will be explored using Pearson's correlation.

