3.3 Description of Study Design

This is an interventional, randomized, double-blind (participant and study staff), sham-controlled, parallel design, pilot study of N=80 RR-MS and SP-MS participants, characterized by mild to moderate gait dysfunctions. There will be a 1:1 random assignment of participants to receive either the active or the sham tDCS while performing the PA program. Blocked stratification will be used to randomize the participants to their respective study conditions. Block sizes of 4 and 6 will be used and the stratifying factor will be EDSS score (0-3.5 and 4.0-6.5). Randomization will be done by an independent randomizer who takes no part in baseline, follow-up, or sessions to maintain the double-blind nature of the study.

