3.4.3 Exploratory Study Endpoint

As an optional measure, we will collect participants' electronic medical records, including MRI brain scans already collected during previous clinical visits, to evaluate whether there is a correlation between the degree of brain atrophy and the participants' clinical response to tDCS i.e., the level of improvement in gait, balance and cognitive measures after tDCS treatment. Previous studies showed inter-individual variability in response to tDCS treatment. One of the factors that affects biological response to electrical current was shown to be the degree of brain atrophy [Lucia et al., 2015; Mahdavi et al., 2018]. Recent studies based on human head model showed how brain characteristics such as total brain and grey matter volume can perturb the current distribution density throughout the brain [Mahdavi et al., 2018]. Specifically, reduced grey matter volume was associated with low magnitude of current density in the brain.

4 Study Enrollment and Withdrawal

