7.2.2 Analysis of the Primary Efficacy Endpoint(s)

Gait speed and Stride length

- Continuous variable (repeated measure)
- The Shapiro-Wilk test will be performed: histograms will be constructed, and measures of central tendency and dispersion will be calculated to test the assumption that distribution is normal
- If normality check will fail a transformation of the data will be done as corrective procedures (transformation will be made according to data distribution)
- Repeated-measures analysis of variance (RM-ANOVA) with tDCS (2 levels: Active and Sham) as the between-independent variable and Time (3 levels: Day 1, Day 10, and After 4-weeks) as the within-independent variable. In the inferential tests statistical significance will be set at 5% and all p-values is two-sided.

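### The exploratory MRI correlation does not use the randomised arm, so it cannot separate response to tDCS from response to exercise or general prognosis

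*Combined protocol and SAP*

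**What the plan says.** Section 3.4.3 (Exploratory Study Endpoint) sets the aim: "to evaluate whether there is a correlation between the degree of brain atrophy and the participants' clinical response to tDCS". It goes on to equate that response with "the level of improvement in gait, balance and cognitive measures after tDCS treatment". The reason given is physical: lower grey matter volume goes with lower current density in the brain. The data are optional ("As an optional measure, we will collect participants' electronic medical records") and the scans are ones already taken at earlier clinical visits.

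Section 7.2.6 gives the analysis. Total brain volume, white and grey matter volume and degree of atrophy are related to "the participant's level of improvement (e.g. % change in gait and balance parameters such as walking speed and sway area", and this "will be explored using Pearson's correlation". Arm is not mentioned: the section does not restrict to active participants, split by arm or include an interaction.

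On the design, section 3.3 states: "There will be a 1:1 random assignment of participants to receive either the active or the sham tDCS while performing the PA program". The primary analysis in section 7.2.2 is an RM-ANOVA "with tDCS (2 levels: Active and Sham) as the between-independent variable", and the listed secondary analyses in 7.2.3 carry the same factor. Section 7.2.6 does not.

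**The concern.** Response to tDCS is what the current adds beyond what the same participant would have achieved with sham and the same exercise. A participant's own before-to-after improvement is not that quantity. In either arm it contains response to ten sessions of cycling, practice on the gait and balance tests, and natural variation. Participants with less atrophy may improve more with exercise whether or not current flows.

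The current-density rationale in 3.4.3 makes a sharper prediction: the relation between atrophy and improvement should differ between active and sham. A single correlation that leaves arm out does not examine that difference. At stake is the interpretation of an exploratory finding. An association between atrophy and exercise response could be read as atrophy predicting who benefits from stimulation, and a real relation confined to the active arm could be diluted. The sham data needed to tell these apart are collected anyway.

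**Working it through.** **No figure to reproduce.** The documents give no sample size, expected correlation or power for this analysis. What follows is an illustration.

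**Inputs from the documents.** Section 4.5: 80 enrolled, 10% dropout, 72 evaluable. Section 3.3: 1:1 allocation, so 72 / 2 = 36 per arm. Section 7.2.1: two-sided 5% for inferential tests.

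**Assumptions.** The correlation r between MRI measure and improvement (0.4, with 0.3 as a second value). The number with MRI: all 36 per arm, or half of them, 18 per arm.

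**Formulas** (Fisher z approximation; Φ is the standard normal distribution function):
- One correlation in n participants: power ≈ Φ(atanh(r) × √(n − 3) − 1.96).
- Difference between two arms of m each: power ≈ Φ(|atanh(r₁) − atanh(r₂)| / √(2/(m − 3)) − 1.96).

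**Case A: atrophy is purely prognostic, r = 0.4 in both arms, tDCS plays no part.** atanh(0.4) = 0.424.
- Pooled, n = 72: 0.424 × √69 = 3.52; Φ(1.56) = 94%.
- Active only, n = 36: 0.424 × √33 = 2.43; Φ(0.47) = 68%.
- Interaction: the true difference is zero, so the test rejects at its nominal 5%.

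Simulation of 20,000 trials gave 94%, 69-70% and 5%. If the arms also differ in mean improvement by 0.85 SD, the pooled figure is 90%. At r = 0.3 the simulated figures are about 70-73%, 43-44% and 5%.

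**Case B: the relation exists only under active tDCS, r = 0.4 active and 0 sham.**
- Pooled: the correlation shrinks to about (0.4 + 0)/2 = 0.2; atanh(0.2) × √69 = 1.68; Φ(−0.28) = 39%.
- Active only: as in case A, because the active-arm data have the same distribution.
- Interaction: 0.424 / √(2/33) = 1.72; Φ(−0.24) = 41%. Simulation gave 39-40%.

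**Half with MRI, 18 per arm.**
- Case A pooled, n = 36: 68% by formula, about 70% simulated.
- Case A active only, n = 18: 0.424 × √15 = 1.64; Φ(−0.32) = 37%, about 38% simulated. Interaction 5%.
- Case B interaction: 0.424 / √(2/15) = 1.16; Φ(−0.80) = 21%, about 20% simulated.

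| Chance of a significant result | Pooled | Active only | Arm × MRI |
|---|---|---|---|
| A, 36 per arm | 94% | 69% | 5% |
| A, 18 per arm | 70% | 38% | 5% |
| B, 36 per arm | 35-39% | 69% | 38-40% |
| B, 18 per arm | about 22% | 38% | 20% |

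The active-only column is the same in A and B, so that test cannot tell the two situations apart. The pooled test is significant more often when tDCS is irrelevant (A) than when it is the whole explanation (B). Only the interaction rises from its nominal level in A to something higher in B.

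**The case against.** **Section 7.2.6 does not say that the arms are pooled.** A reader might infer that the plan mixes active and sham participants in one correlation. The text is silent on arm, and the wording of 3.4.3 about improvement following tDCS can be read as active participants only. This stands, and the point is therefore not that the plan pools. It is that neither reading brings in the sham contrast. The silence also leaves the choice open until the data are seen.

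**The question is answered as literally defined.** Section 3.4.3 asks about a correlation and defines response as level of improvement, which 7.2.6 does correlate. That is fair as far as it goes. But the definition lacks a sham comparison, and the rationale beside it concerns current reaching the brain, which a sham-blind correlation does not test.

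**The percentages rest on assumptions.** They do: no correlation or MRI count is in the documents. The contrast between methods does not depend on the exact r.

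**The active-only correlation has more power.** True in case B: about 69% against 38-40%, and 38% against 20% with half the MRI data. That is the real price of the interaction. The extra power comes without the ability to attribute the relation to tDCS.

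**Percent change has baseline in its denominator.** One might infer that this alone would manufacture an association. The documents do not support so strong a claim: percent change is only an example in 7.2.6, and no atrophy-baseline correlation is given. It is a minor matter.

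**The analysis is optional and exploratory.** This stands and sets the severity.

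**Conclusion.** The point holds in limited form. The exploratory question concerns response to tDCS, and the planned analysis omits the one variable, randomised arm, that could isolate it. Read as pooled or as active-only, the analysis cannot separate tDCS response from exercise response, practice or prognosis. Under the assumed purely prognostic scenario with r = 0.4, a significant correlation appears in about 94% (pooled) or 69% (active-only) of trials at 36 per arm, and in about 70% or 38% at 18 per arm, against 5% for an interaction test. These sizes depend on the assumed correlation and MRI availability.

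A reader might go further and conclude that the trial's efficacy findings are affected, or that a false claim of prediction will be published. The documents support neither. The primary and listed secondary analyses carry the arm factor and do not depend on 7.2.6, and the plan calls this analysis exploratory. Severity is low; it is a cheap improvement.

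**What to change.** In 7.2.6, for each outcome family named in 3.4.3 (gait, balance and cognitive), specify a linear model of the treatment-end value on its baseline value, arm, MRI measure and arm × MRI measure. EDSS stratum may be added, since it is the randomisation factor. Report the interaction with its 95% CI and the slope or correlation within each arm, all labelled exploratory. State the number with MRI in each arm.

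Using baseline as a covariate also removes the division by baseline, a small secondary gain. Naming the cognitive outcomes brings 7.2.6 into line with 3.4.3, since its present examples cover only gait and balance.

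The cost is SAP wording. Arm, baseline and EDSS are already held, and no further participants, visits or scans are needed. The downside should be written into the plan: the interaction will be imprecise, with power of about 38-40% at 36 per arm and about 20% at 18 per arm for a correlation of 0.4 confined to the active arm. A non-significant interaction is therefore not evidence that atrophy is irrelevant, and the interval should carry the interpretation.

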7.3 Sample Size

The sample size is calculated on the primary endpoint gait velocity measured before tDCS treatments at baseline time in a population of individuals affected by MS (0.98 ± 0.23 m/s). According to previous study the variability of changes after tDCS combined with PA is on average around 20% in active group compared with baseline assessment.

To recognize as significant change in gait velocity (alpha level = 0.05), equal to 20% difference between baseline and end of the treatment, a sample size of 19 cases for each arm will provide a power of 80%.

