Given that MS is a chronic, long-lasting and disabling disease, physical training plays an important role in maintaining an independent lifestyle and good quality of life [Takemasa et al., 1998]. The goal is to minimize functional disability and optimize functional motor recovery. Exercise training, like cycling or treadmill protocol, is a planned, structured, and repetitive PA, and if undertaken over time, can lead to improved physical fitness [Bouchard et al., 1994]. Exercise training has been considered the most effective nonpharmacological treatment in MS with robust evidence for improvements in walking outcomes [Snook et al., 2009; Dalgas et al., 2014; Pearson et al., 2015]. However, current protocols generally achieve only limited recovery of motor impairments [Sutliff et al., 2016]. Thus, there is the need to develop new methods capable of enhancing the effects of rehabilitation therapies.

Recently, considerable attention has been drawn to non-invasive brain stimulation (NIBS) to help the brain to reach an optimal state of activity to facilitate subsequent training effects. Recent studies reported that the

CONFIDENTIAL

This material is the property of the NYU School of Medicine and Langone Medical Center. Do not disclose or use except as authorized in writing by the study sponsor
Interventional Template Version: 28 APR 2017

positive effects of physical activities might be potentiated by NIBS and that it has the potential to be considered an adjuvant tool able to enhance the rehabilitation effects.

Transcranial direct current stimulation (tDCS) is a non-invasive treatment option that has been found to reduce the intensity of a wide array of symptoms in neurological disorders such as Parkinson's disease, cerebral palsy, stroke, multiple sclerosis, and depression among others. The effects of tDCS are thought to be mediated through alterations of the resting potential of neurons via distribution of direct electrical current. A mild electrical current ($\approx 2\text{mA}$) is typically applied through electrodes placed on the scalp. It is a relatively inexpensive treatment modality that has been shown to be safe and tolerable in many clinical populations.

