3.4 Study Endpoints

3.4.1 Primary Study Endpoints

To determine the efficacy of the combination of tDCS and physical training, the following primary outcome measures have been chosen:

- Efficacy measured by comparison between the active and sham conditions by comparing the changes in gait velocity and stride length at baseline and participation end
- Compliance measured by 80% of participants having completed the study sessions

CONFIDENTIAL

This material is the property of the NYU School of Medicine and Langone Medical Center. Do not disclose or use except as authorized in writing by the study sponsor

Interventional Template Version: 28 APR 2017

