4.9 Study Procedural Intervention Description

4.9.1 Administration of Procedural Intervention

Study technicians trained to oversee tDCS sessions will administer the tDCS treatments. Training includes familiarity with the device and all of its safety features. Furthermore, technicians will be trained to properly oversee the physical activity sessions to ensure a safe environment.

Procedure for the administration of the treatment:

Electrodes preparation: the $5 \times 5 \text{ cm}^2$ carbon rubber electrodes work with saline solution in order to increase conductance. Inject 5 ml of saline solution on the external surface of the carbon rubber of each electrode.

Electrodes montage: The carbon rubber sponge electrodes will be placed according to the International 10-20 EEG System. The anodal electrode will be attached at Cz position on the scalp, which corresponds to the lower limb motor cortex. The cathodal electrode will be attached at the supraorbital area on the forehead. Before starting stimulation session check the impedance. Study technicians will troubleshoot the connection if the impedance is high enough that the device cannot reliably stimulate.

Arm 1: Active tDCS and physical training

Participants will receive active tDCS while performing physical training (see detailed description in Section 6.3). A direct current of 2.5 mA will be applied throughout the stimulation session.

Arm 2: Sham tDCS and physical training

Participants will receive a sham tDCS while performing physical training (see detailed description in Section 6.3). During a sham session, the device is programmed to ramp up to the desired intensity (target 2.5 mA) and ramp down for the initial 60 seconds, with no current delivery during the session, and then again at the end of the session. These brief periods of stimulation serve to mimic the effects of a true stimulation session.

Schedule of the intervention procedure: 20 minutes of active/sham stimulation, once daily, scheduled for 10 business days over the course of approximately two weeks. The participant will be able to compensate for any missed session the week after to complete a total of 10 visits. The total duration of the treatment will be approximately 3.3 hours (20 mins x 10 sessions).

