7.1 Statistical Hypotheses

Research hypothesis

There is a significant difference between active and sham groups by comparing primary and secondary outcomes at baseline and end treatment time.

Null hypothesis

There will not be a significant difference between active and sham groups

CONFIDENTIAL

This material is the property of the NYU School of Medicine and Langone Medical Center. Do not disclose or use except as authorized in writing by the study sponsor

Interventional Template Version: 28 APR 2017

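### The 19-per-arm, 80% power statement in Section 7.3 does not follow from its printed inputs, gives no active-versus-sham effect, and does not support the planned 80 enrolled

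*Combined protocol and SAP*

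**What the plan says.** Section 7.3 bases the calculation on "gait velocity measured before tDCS treatments at baseline time in a population of individuals affected by MS (0.98 ± 0.23 m/s"). It adds that "the variability of changes after tDCS combined with PA is on average around 20% in active group compared with baseline assessment", and takes a 20% difference from baseline to end of treatment as the target at alpha 0.05. It concludes that "a sample size of 19 cases for each arm will provide a power of 80" percent. It names no test, sidedness, SD of change, correlation or sham-arm change, and it does not mention dropout, 72 or 80.

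Other sections set the context:

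- Section 3.4.1 defines the primary efficacy endpoint as active versus sham, "comparing the changes in gait velocity and stride length at baseline and participation end".
- Section 7.1 states the hypothesis: "There is a significant difference between active and sham groups by comparing primary and secondary outcomes at baseline and end treatment time".
- Section 4.9.1 says of the control arm: "Participants will receive a sham tDCS while performing physical training".
- Sections 7.2.1 and 7.2.2 set two-sided tests at 5% and a group-by-time repeated-measures ANOVA with "Time (3 levels: Day 1, Day 10, and After 4-weeks) as the within-independent variable".
- Section 4.5 plans about 80 enrolled and 72 evaluable after 10% dropout, and refers to the sample size estimation.

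**The concern.** This is the plan's only power statement, and it fails in three ways.

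1. The printed inputs do not give 19 per arm at the two-sided level the plan sets.
2. The effect is a change from baseline within the active arm, from a previous study whose population is not named. Applying the resulting per-arm number to an active-versus-sham comparison implies that sham plus exercise changes nothing, which the plan never states. Section 2.1 credits exercise training with walking gains and then says "current protocols generally achieve only limited recovery of motor impairments", so it fixes no value for the sham change.
3. Section 4.5 sends the reader to Section 7.3 for numbers that are not there.

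At stake is how the result can be read. The confidence interval from a null trial could be set against the 20%, but that is a within-arm figure. The plan states no between-arm difference that 36 per arm is meant to detect.

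**Working it through.** **Inputs.** From Section 7.3: mean 0.98 m/s, SD 0.23, change 20%, alpha 0.05, power 80%, 19 per arm. From Section 7.2: two-sided tests. From Section 3.3: 1:1 allocation. From Section 4.5: 80 enrolled, 10% dropout, 72 evaluable.

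**1. Trying to reproduce 19 per arm.** The difference is 0.20 × 0.98 = 0.196 m/s, so d = 0.196 / 0.23 = 0.852.

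- Normal approximation, two-sided: n = 2 × (1.960 + 0.842)² / 0.852² = 21.6, so 22 per arm. Power at 19 is 74.7%.
- Two-sample t-test, two-sided (noncentral t): n = 22.6, so 23 per arm. Power at 19 is 72.4%, and at 23 it is 80.7%.

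Routes that do reach 19, or come close, each need something the plan does not state:

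| Route | Unstated element | n per arm |
|---|---|---|
| t-test on change scores, two-sided | correlation 0.584 to 0.607 | 19 |
| ANCOVA, two-sided | correlation 0.411 to 0.464 | 19 |
| Paired test within one arm, two-sided | correlation 0.214 to 0.260 | 19 |
| One-sided t-test | contradicts Section 7.2 | 17.7, so 18 |
| One-sided rank test (efficiency 3/π = 0.955) | contradicts Section 7.2 | 17.7 / 0.955 = 18.6, so 19 |

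**2. From 19 per arm to the planned size.** 2 × 19 = 38 evaluable. With 10% dropout, 19 / 0.9 = 21.1, so 22 per arm and 44 in total. Section 4.5's own arithmetic is correct (80 × 0.9 = 72), but 72 does not come from 19 per arm.

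**3. What 36 per arm can detect.** Assume SD 0.23 at each visit and baseline-to-end correlation r, which the documents do not give.

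- SD of change = 0.23 × √(2(1 − r)).
- Difference detectable with 80% power, two-sided 5% t-test, 36 per arm = 0.6696 × SD of change.
- 95% CI half-width = t(0.975, 70 df) × SD of change × √(2/36).
- If the active arm changes by 0.196 m/s, the largest sham change that keeps 80% power = 0.196 minus the detectable difference.

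| r (assumed) | SD of change | Detectable difference, m/s (% of 0.98) | 95% CI half-width, m/s | Largest sham change, m/s (% of 0.98) |
|---|---|---|---|---|
| 0.5 | 0.230 | 0.154 (15.7%) | 0.108 | 0.042 (4.3%) |
| 0.6 | 0.206 | 0.138 (14.1%) | 0.097 | 0.058 (5.9%) |
| 0.7 | 0.178 | 0.119 (12.2%) | 0.084 | 0.077 (7.8%) |
| 0.8 | 0.145 | 0.097 (9.9%) | 0.068 | 0.099 (10.1%) |

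For a true between-arm difference of 0.196 m/s, 36 per arm gives 94.6% power when the SD of change is 0.23, that is, at r = 0.5.

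**4. The test matters.** A simulation (20,000 runs, 36 per arm, equal correlations, no missing data) set the end-of-treatment difference at the detectable value. The baseline-to-end contrast had 80% power. The three-level interaction F-test had about 84% if the effect was fully kept or fully lost at 4 weeks, and about 71% if half was kept. A power figure therefore needs a named test.

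**The case against.** The strongest reply is that part one shows under-specification rather than an error. Section 7.3 names no test and speaks of a change over time, so an independent-samples test on a cross-sectional SD may not be what was run, and 19 is compatible with a two-sided 5% test at a plausible correlation. This stands in part. Nobody can show which calculation was done, and 19 is not impossible. But the figure cannot be obtained from what is printed, and several incompatible routes lead to it.

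The wording about variability of changes could also mean that the SD of change is 20%, or 0.196 m/s. A difference of 0.196 then has d = 1, which needs 17 per arm and gives 85% power at 19. On that reading 19 would be enough, but it still would not be the calculated number, and the sentence that follows in Section 7.3 treats the 20% as the change to detect.

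It is also fair that this is labelled a pilot with a compliance co-primary, and that enrolling more than a calculated minimum contradicts nothing. Neither point supplies the missing between-arm effect, and the plan still makes an efficacy claim with a 5% test and 80% power.

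Finally, the 36-per-arm figures assume complete data. The 4-week visit is marked optional in Sections 4.4 and 16, so a complete-case three-level ANOVA could lose participants. This stands, and it is a further reason to tie the power statement to the baseline-to-end contrast.

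**Conclusion.** The concern holds; it should be fixed. On the printed inputs at two-sided 5%, a two-sample t-test needs 23 per arm rather than 19, and 19 gives 72% power rather than 80%. The 20% is a within-arm change, so no active-versus-sham effect is stated. The calculation supports 38 evaluable, about half of the 72 for which Section 4.5 cites it.

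This does not show an underpowered trial, since 72 evaluable exceeds the 46 (2 × 23) needed for 0.196 m/s. What 36 per arm can detect between arms depends on two inputs the plan omits: the baseline-to-end correlation (or SD of change) and the change expected under sham plus exercise. Over assumed correlations of 0.5 to 0.8, the detectable difference runs from 0.154 to 0.097 m/s. If the active arm does improve by 20%, power falls below 80% once the sham arm improves by more than 4.3% to 10.1% of baseline.

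**What to change.** - **Section 7.3.** Replace the 19-per-arm statement with: *With 36 evaluable per arm (80 enrolled, 10% dropout), a two-sided 5% test of the active-versus-sham difference in change in gait velocity from baseline to treatment end has 80% power to detect X m/s, assuming SD 0.23 at each visit and baseline-to-end correlation r.* X is 0.154, 0.138, 0.119 or 0.097 at r = 0.5, 0.6, 0.7 or 0.8. The sponsor must give a source for r.
- **Also in Section 7.3.** State the change assumed under sham plus physical activity. Say whether the 20% is a mean change or a spread of changes, label it as within-arm, and name its source and population.
- **Section 7.2.2.** Name the baseline-to-end group-by-time contrast as the test of the gait velocity endpoint in Section 3.4.1.
- **Section 4.5.** Point the cross-reference to the new statement.

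The cost is one rewritten paragraph, one added sentence and one corrected line, with no extra participants. The sentence in 7.2.2 is a small but real change to the analysis text, because it specifies a test the plan now leaves open. The downside is that the power figure will then visibly depend on an assumed correlation and sham-arm change.
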